9.5. Randomisation

Infants will be randomised using minimisation incorporating the following variables: hospital site, gestation (<25 weeks: ≤ 24 weeks and 6 days), and multiple birth status; this will be held and coordinated by the Newcastle research team using an internet based secured randomisation system, and will include strata for hospital site, gestation (<25 weeks and ≥ 25 weeks gestation), and multiple birth status. Contact and allocation will be by password protected internet access. Infants will be allocated to either standard diet (control) or the exclusive human milk-based diet (intervention). Multiples (twins and higher order) will be randomised independently.

9.6. Patient withdrawal

9.6.1. Temporary discontinuation of intervention

There should be no reason to discontinue trial intervention before the infant achieves milk feeds of at least 150 ml /kg /day. In exceptional circumstances however, a temporary discontinuation of the intervention could occur at any point during the intervention period for e.g. feed intolerance. It is unlikely that there will be problems with compliance with the interventions.

9.6.2. Permanent discontinuation of intervention

Parents may permanently withdraw their infant from treatment with the trial intervention at any time and for any reason.

565	9.6.3. Withdrawal of infant from trial procedures and incomplete follow-up
566	It is possible that parents may choose to withdraw their infant from trial procedures resulting
567	in incomplete patient follow-up and failure to capture outcome data. Likewise, if an
568	infant dies before discharge they will not have their MRI scan. In these cases data
569	already obtained will be included in all analyses.
570	
571	10. TRIAL PRODUCTS
572	10.1. Description
573	• Ready to Feed Human Preterm 26 formula (Prolacta): Constituted from term human
574	donor milk, each 100 ml provides 90 kcal of energy, 2.6 g of protein, 8.1 g of
575	carbohydrate and 5.2 g of fat. Appendix 2.
576	• Human milk based fortifier, Prolact+6 (Prolacta): Appendix 3
577	• Standard preterm formula: SMA Gold Prem 1 or Nutricia Nutriprem 1 (Appendix 4
578	and 5)
579	• Standard fortifier Nutriprem (Nutricia) (Appendix 6)
580	
581	10.2 Labelling
582	This is an open label study. The Prolacta products will be specifically labelled as a food for
583	special medical purposes (i.e., preterm infants) for shipment and courier according
584	Department of Health specifications. Labelling on the bottles will include batch number and
585	nutrient density. Batch numbers will be recorded in infant case records.
586	
587	10.3 Storage
588	The milk products provided by Prolacta are shipped frozen according to carefully established
589	procedures and are stored on or near the neonatal units. Standard Operating Procedures will
590	be used for checking milk on arrival and storage. Bedside clinical nurses will receive training
591	to use the trial products.
592	
593	11. TRIAL OBSERVATIONS, TESTS AND INVESTIGATIONS
594	11.1 Trial data

- 595 We will obtain routinely recorded clinical data from the National Neonatal Research
- Database (NNRD), held at Imperial College London, supplemented by the use of standard
- case report forms where items are not recorded in the NNRD.
- 598 11.2 Time scale for trial evaluations
- 599 11.2.1 Daily stool and urine samples: These will be collected by the bedside nurse from
- admission to 34 weeks postmenstrual age.
- 601 11.2.2 Salvaged blood samples (Newcastle only): We will salvage leftover blood samples
- 602 (blood that remains in the laboratories after all routine analyses have been complete and
- would ordinarily be discarded). These will be stored for biobanking [10].
- 11.2.3 Targeted blood samples (Newcastle only): With specific parent consent (that would
- not otherwise preclude ongoing trial participation) we will also take two targeted blood
- samples: 1) after feeds of 150mls/kg/day have been established for at least 3 days and 2) prior
- to trial cessation i.e. around 33-34 weeks postmenstrual age. Targeted blood samples will be
- taken at the same time as any blood samples required for clinical reasons so will not involve
- additional venepuncture.
- 610 11.2.4 Body Composition (Imperial only): at 37-42 weeks postmenstrual age assessed with
- 611 whole body MRI

- 613 11.3 Data
- 614 11.3.1 At randomisation
- Date and time of birth
- 616 Sex
- Confirmation of eligibility (full eligibility check)
- Date of parental consent
- Name of person taking consent
- Gestational age (in weeks and days)
- Recruiting hospital
- 622 Study allocation
- 623 11.3.2 Baseline evaluation
- Birth weight (kg)

625 Birth length (cm) • 626 Head circumference (cm) 627 Ethnicity (NHS Ethnicity) 628 Mode of delivery 629 Use of antenatal steroids 630 Date and time first trial intervention administered 631 11.3.3 Daily evaluations 632 Record nutritional intake (type of feed, parenteral nutrition or formula as applicable) • 633 Level of care (BAPM 2010) 634 If infant is nil by mouth and reason 635 Check for SAE 636 Record of withdrawal information if relevant 637 11.3.4 Weekly evaluations 638 Weight (kg) 639 Length (cm) 640 Head circumference (cm) 641 11.3.5 End of study evaluation 642 Weight (kg) 643 Length (cm) 644 Head circumference (cm) 645 Whole body MRI 646 647 11.4 Investigations 648 11.4.1 Stool microbiome

We will analyse bacteria DNA extracted from stool samples using our well-established protocols and 16S ribosomal RNA methods that are effective tools to explore the diversity of bacterial communities (Stewart et al. 2012). Using the MiSeq high throughput analyzer we will incorporate 188 samples as well as necessary controls, which we have found to be the optimum number of samples to obtain coverage of the bacterial community.

654

11.4.2 Urine and stool metabolome and biochemical assays

We will conduct metabolomic profiling of urine and/or stool. Extraction of samples will be optimised for detection of SCFAs and samples processed using non-targeted and targeted high-resolution liquid chromatography-mass spectroscopy (LCMS) to generate metabolomic profiles that may indicate functional changes in the host and the gut microbiota. Our targeted approach will investigate known gut flora fermented products of complex carbohydrates, including SCFAs, acetates, amino acids and CHO fragments, which will be present in stool samples. Analysis (see statistics section below) will use modeling techniques to explore relationships between the microbiome and metabolome, and diet. Examination of the urinary metabolome is more reflective of changes to the overall host (infant) metabolic state but may also reflect differences in absorption of compounds from the gut. Determining the metabolomic profiles between and within patients to complement the NGS sequencing data will provide significant opportunities to develop quantitative models that show how the host, gut microbes, trial interventions and other clinical factors interact, and any downstream functional effects.

669670

671

672

673

655

656

657

658

659

660

661

662

663

664

665

666

667

668

We will also analyse some urine and stool samples using assays for proteins that may indicate gut health including fecal calprotectin and urinary intestinal fatty acid binding protein. These will provide additional insight into any gut inflammatory processes and the integrity of gut epithelium.

674 675

676

11.4.3 Stool metabolomics and VOC analysis

- VOCs from stool samples will be analysed by GC/MS using well-established protocols for
- extracting and analysing headspace gases. These are validated on as little as 50mg of sample:
- sufficient to analyse ~40 compounds, which includes 8 different acids, particularly SCFAs,
- branched and linear, alcohols and esters. Interpretation of fragment patterns will be
- undertaken against the current mass spectral NIST library, followed by manual visual
- inspection. Standards will be purchased for retention time matching. Summary data of the
- abundance of acids, alcohols and esters will be determined and prepared for statistical
- 684 analysis

685

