1. PROTOCOL SUMMARY

Title (Acronym)	In teractions between the di et and g ut microbes, metabolism and body composition in preterm infants (INDIGO)
Study centres	Newcastle Royal Infirmary and Chelsea and Westminster NHS Foundation Trust (Imperial College London). Additional sites may be added
Study objectives	To evaluate whether an exclusive human milk diet compared with exposure to cow's milk-based products results in differences in a) gut bacteria (types and diversity, b) stool and urine metabolites and c) body composition
Study design	Randomised open label, controlled trial
Study population	 Inclusion criteria Preterm infants born below 30 completed weeks of gestation (≤ 29 weeks and 6 days) <72 hours age Written informed consent from parents Exclusion criteria Major congenital or life-threatening abnormalities Inability to randomise within 48 hours of birth Exposure to bovine milk product prior to randomisation Likelihood of transfer to another hospital before 34 weeks postmenstrual age
Interventions	• Exclusive human diet (human donor milk and human milk-based fortifier: 'Prolacta RTF 26' and 'Prolacta 6')
Route of administration	Enteral
Target number of patients	At least 100 patients to provide ~80 evaluable infants in total with stool samples for microbiome analysis at 34w PMA
Randomisation	 Using minimisation incorporating the following variables: hospital site, gestation (<25 weeks: ≤24 weeks and 6 days), and multiple birth status Secured, password protected web-based randomisation using minimisation algorithm (www.sealedenvelope.com or similar)
Primary outcomes	 Microbiota: gut bacterial diversity, proportions of specific taxa, e.g. Bifidobacteria species Body composition; adipose tissue mass and non-adipose tissue mass assessed using whole body magnetic resonance imaging (MRI) at term (37-42 weeks postmenstrual age)
Secondary outcomes	Metabolome: Gut derived metabolites and markers of gut function; metabolites include stool Volatile Organic Compounds (VOC, using Gas Chromatography MS), and urine (e.g. using 1H NMR and/or Liquid Chromatography MS); markers of gut health may include those measured in the stool (e.g. calprotectin) and urine (e.g. intestinal fatty acid binding protein, iFABP) Feed and nutrition related outcomes Healthcare resource use Neonatal morbidities and clinical outcomes Adipose tissue volume and distribution
Duration of trial intervention	To 34 weeks postmenstrual age

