8. TRIAL ENDPOINTS

- The outcomes assessed in infants recruited at both sites will be microbiota and metabolomics.
- 438 Infants recruited at Chelsea and Westminster NHS Foundation Trust will be additionally be
- 439 assessed for body composition. Infants recruited in Newcastle will have additional blood
- samples collected and stored for future studies.

441

420

421

422

423

424

425

426

427

428

429

430

431

432

433

434 435

436

- 442 8.1. Primary endpoints
- 8.1.1. Newcastle and Chelsea and Westminster NHS Foundation Trust Hospitals
- 444 8.1.1.1. Stool gut microbiota: Next Generation Sequencing using MiSeq
- 445 8.1.2. Chelsea and Westminster NHS Foundation Trust (Imperial College London)
- 8.1.2.1. Body composition at term equivalent age assessed with whole body Magnetic
- Resonance Imaging (MRI) at 37-42 weeks postmenstrual age
- 448 **8.1.3.** Newcastle
- 8.1.3.1. Salvaged blood for growth factors e.g. IGF-1
- 450 8.1.3.2. Targeted blood: plasma amino acid (PAA) profiles and lymphocyte subsets.

- 452 8.2. Secondary endpoints
- 453 8.2.1.1. Stool metabolomic profile using GC-MS for VOCs
- 454 8.2.1.2. Urine metabolomic profile using LC-MS or NMR
- 455 8.2.1.3. Markers of gut health e.g. urinary intestinal fatty acid binding protein (iFABP)
- and stool calprotectin, using standard biochemical techniques
- 8.2.2. Feeding related outcomes: total number of days on which feeds were withheld on any
- 458 occasion after trial enrolment determined by days of parenteral nutrition (PN); age when
- 459 enteral feeds ≥150ml/kg/day maintained for at least 3 days (coded as age at last PN); total
- days exposed to MOM prior to 34 weeks; feeding mode at discharge (breast, formula or
- 461 mixed)
- 462 8.2.3. Healthcare resource use: total length of stay (days); postmenstrual age at discharge;
- 463 days in intensive, high-dependency and low-dependency care according to national
- 464 definitions (BAPM)
- 8.2.4. Neonatal morbidities and clinical outcomes: survival to discharge; Retinopathy of
- 466 Prematurity requiring intervention; Necrotising Enterocolitis requiring surgery or leading to
- death; blood-culture positive sepsis; total days when any antibiotic administered; chronic
- 468 lung disease (oxygen requirement or need for any pressure support at 36 weeks postmenstrual
- age), peri-ventricular haemorrhage (PVH) and/or presence of parenchymal damage. These

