- Using 16S rRNA bacterial profiling data we will conduct alpha and beta diversity analysis. Based on previously published data by our group[12,13] a Shannon Diversity Index alpha diversity of <1 is representative of infants in the initial weeks of life where the microbiome is undeveloped; a Shannon Diversity Index of >1.5 is representative of infants immediately prior to neonatal unit discharge where the gut microbiome is more developed and risk of gut microbiome mediated disease is significantly reduced. Based on these findings a sample size of 24 in each group (48 in total) is required to achieve over 95% power detect a 0.5SD difference in diversity index. By processing 40 samples in each group we will reach this power for true significance of alpha diversity analysis and note from previous analysis that that this number is also sufficient for beta diversity analyses, including but not limited to UniFrac distance, clustering (PAM and DMM), correlation (CCLasso), ordination analysis (PCA and PCoA), and determining significant differences between the relative abundance of different genera.
- 746 13.1.2 Body composition

Supplementary materials Effect of an exclusive human milk diet on the gut microbiome in preterm infants; a randomised clinical trial

We will compare proportions of key taxa e.g. proteobacteria, firmicutes etc., as well as

numbers and presence of key species including lactobacilli, bifidobacteria and staphylococci.

- In our most recent work in preterm infants born at <31 weeks gestational age, the mean (SD)
- of non-adipose tissue mass was 2.41 (0.46) kg (Uthaya et al. 2016)[14]. A sample size of 20
- 549 babies per group will have 80% power at the 5% significance level (2-sided) to detect a 0.42
- 750 kg between-group difference in non-adipose tissue mass assessed by whole body Magnetic
- 751 Resonance Imaging using protocols previously described[15,14].

752 13.1.3 Metabolome

- 753 Stool VOC analysis identifies several individual compounds; our collaborators show an
- average 31.3±10.5 (Mean and SD) VOCs were identified per sample [16]. With n=40 infants
- per group we will have 85% power to detect an increase in 5 VOCs between intervention and
- standard groups. Urinary 1H NMR studies are limited in preterm infants. However, highly
- 757 significant differences in spectra (p<0.005) were detected between adults born preterm
- 758 (n=19) and term (n=17). The differences observed were in key metabolites such as

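### The 85% power for stool VOCs is stated for a compound count, while the data prepared for analysis are class abundances, and the figure is not met for the count either

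*Protocol*

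**What the plan says.** Three places in the protocol bear on the stool VOC outcome.

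- **Endpoint (8.2.1.1, secondary):** "Stool metabolomic profile using GC-MS for VOCs". Neither a count nor an abundance is named.
- **Assay (11.4.3):** after describing the extraction and identification of compounds, the section says that summary data on the "abundance of acids, alcohols and esters will be determined and prepared for statistical" analysis. This is an amount by chemical class.
- **Power (13.1.3):** the claim, made for 40 infants in each arm, is "per group we will have 85% power to detect an increase in 5 VOCs between intervention and" control. The planning values behind it, a mean of 31.3 and an SD of 10.5, are likewise counts of compounds found in a sample.

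Section 13.1.3 gives no significance level or sidedness for VOCs. The body composition calculation in 13.1.2 does: "babies per group will have 80% power at the 5% significance level (2-sided) to detect a 0.42" kg difference. Section 11.4.2 points ahead to a statistics section for the metabolome analysis, but section 13.2 covers only microbiome, body composition and missing data.

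**The concern.** How many compounds are found and how much of each class is present are different variables. Total acid or ester can shift with no new compound detected, and compounds can appear or vanish at trace level with little effect on class totals. A power statement for one says nothing about the other unless the other's SD and target difference are also given, and here they are not.

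What is at stake is how a VOC result is read. If the abundance comparison shows no difference, a reader of 13.1.3 may take that null as backed by 85% power. If the count is compared, the same reader would still be relying on a power well above what the stated inputs deliver.

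**Working it through.** **Inputs.** From 13.1.3: SD 10.5, difference 5, n = 40 per group, stated power 85%. Assumed: a two-sample comparison at two-sided 5%, the level that 13.1.2 gives for body composition. Other levels are tried below.

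**Step 1: try to reproduce the 85% for the count.**

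Standardised difference: 5 / 10.5 = 0.476.

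Noncentrality: 0.476 × √(40/2) = 2.13.

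Normal approximation, two-sided 5%: power = Φ(2.13 − 1.96) = 0.567.

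| Two-sample test, 40 per group | Power |
|---|---|
| t test, 5% two-sided | 55.7% |
| Normal approximation, 5% two-sided | 56.7% |
| Rank test (efficiency 0.955), 5% two-sided | 54.8% |
| t test, 5% one-sided | 67.9% |
| Normal approximation, 5% one-sided or 10% two-sided | 68.6% |
| Normal approximation, 10% one-sided | 80.2% |

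None of these reaches 85%. The figure does appear in two other settings with the same inputs: a one-sample formula with n = 40, and a two-sample comparison with 80 per group. Both have noncentrality 0.476 × √40 = 3.01 and normal-approximation power Φ(3.01 − 1.96) = 85.4%. The protocol does not say how its figure was obtained, so either origin is a conjecture.

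**Step 2: what 85% would require for the count.**

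n per group = 2 × (1.96 + 1.036)² × 10.5² / 5² = 79.2, so about 80 per group. One-sided 5%: 2 × (1.645 + 1.036)² × 10.5² / 5² = 63.4, so 64 per group.

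With 40 per group held fixed (noncentral t, two-sided 5%):

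- 80% power: 0.634 SD, or 0.634 × 10.5 = 6.7 VOCs
- 85% power: 0.678 SD, or 0.678 × 10.5 = 7.1 VOCs

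**Step 3: what can be said for abundance.** The protocol gives no mean, SD or target difference for the abundance of any class, so no power can be computed. All that follows from n = 40 per group is the detectable standardised difference for one continuous measure in one test: about 0.63 SD at 80% power, two-sided 5%. Acids, alcohols and esters are three classes. Testing each with a multiplicity correction would raise that threshold.

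**The case against.** The strongest reply is that the documents do not set the count aside. Section 13.1.3 words its power as a contrast between the two groups, which implies that the count will be compared. The count comes from the same GC-MS output, and a profile can include it. Section 11.4.3 is a laboratory section that does not limit analysis to abundances, and a SAP that is not shown may define the VOC variables. All of this stands. A reader might infer that the count is never tested. The protocol does not support that. It says only that abundances are prepared for analysis, and it leaves the count unnamed outside the power section.

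A second reply is that no design decision rests on this figure. That also stands. The 40 per group comes from the microbiome calculation in 13.1.1, and the summary ties the target to that outcome: "At least 100 patients to provide ~80 evaluable infants in total with stool samples for microbiome analysis at 34w PMA". Section 13.1.3 starts from 40 and reports a resulting power, so it would be wrong to say that the VOC count justifies the sample size.

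A reader might also argue that the planning values do not fit the assay, since 11.4.3 speaks of a sample "sufficient to analyse ~40 compounds, which includes 8 different acids, particularly SCFAs". On a normal distribution, a mean of 31.3 with SD 10.5 would put many values above 40. The text does not support this either. The figure is an approximate yield at the smallest validated sample mass and not a stated ceiling, and nothing says the count is normally distributed. Even under a hard limit of 40, a variable with mean 31.3 could have an SD as large as √(31.3 × 8.7) = 16.5, so 10.5 is possible.

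None of these replies rescues the 85%. It does not transfer to abundance, and the protocol's own inputs do not yield it for the count.

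**Conclusion.** The point holds in this form: the protocol powers one VOC quantity and describes preparing another for analysis, and the power it states applies to neither. For the count, the planned size gives about 56% and not 85% for a difference of 5, a shortfall of about 29 percentage points. The power is about 68% if the test is one-sided. For abundance, no power is stated and none can be derived.

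The 56% rests on a two-sample comparison at two-sided 5%, an SD of 10.5 in both groups, and 40 evaluable infants in each group. The conclusion that 85% is not reached does not depend on the choice of alpha across the levels tried.

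The consequence is limited. VOCs are a secondary endpoint in a mechanistic trial. The sample size and the primary outcomes are unaffected.

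**What to change.** Reconcile 8.2.1.1, 11.4.3 and 13.1.3 on the VOC variable to be compared between groups, and replace the 85% sentence in 13.1.3 accordingly.

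- **If the count is kept:** name it in 8.2.1.1 and 11.4.3. State about 56% power for a difference of 5 VOCs with 40 per group, or a detectable difference of about 6.7 VOCs at 80% power (about 7.1 at 85%).
- **If abundance is kept:** withdraw the 5-VOC sentence. State that 40 per group detects about 0.63 SD with 80% power for a single comparison.

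In either case, give the significance level and sidedness. The sentences above assume two-sided 5%.

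The cost is wording only. Recruitment, sampling and assays do not change. The one real loss is that the protocol can no longer claim 85% power for this outcome.

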11.4.4 Blood analyses (Newcastle site only)

- We will store salvaged blood with parental permission to analyse in future studies examining immune (e.g. specific antibody) and inflammatory pathways, and to conduct e.g. epigenetic
- analysis e.g. DNA methylation. Targeted blood samples will be analysed for
- Flow cytometry to determine lymphocyte subset proportions.
 - Plasma amino acid profiles
 - If sample volume allows we will consider analyses of additional markers of gut health include for example cytokines

11.4.5 Body composition (Chelsea & Westminster site only)

We will use whole-body MR imaging to obtain serial axial images (5mm slice and inter-slice thickness) to quantify total adipose tissue (AT) volume as the sum of 6 discrete depots: superficial subcutaneous abdominal, superficial subcutaneous non-abdominal, deep subcutaneous abdominal, internal abdominal (IA), and internal non-abdominal, as previously described (Modi et al. 2009).[11] Image analysis with the use of Slice-OMatic (Tomovision) will be undertaken independently blinded to participant identity and group allocation. AT volume in litres will be converted to AT mass in kg, assuming a value for the density of AT of 0.90 kg/L. Non-AT mass is calculated by subtracting AT mass from the weight of the infant on the day of the MR scan using the following formula: [body weight (g) - [AT volume (cm³) × 0.9]]. MR scanning will be carried out in natural sleep between 37-42 weeks postmenstrual age.

